controlled design with 374 cancer patients, we will: 1) Compare standard varenicline treatment (12-weeks active + 12-weeks placebo) to extended varenicline treatment (24-weeks active) for increasing week 24 and week 52 biochemically-confirmed 7-day point prevalence abstinence; 2) Assess the effects of extended varenicline therapy on QOL, including varenicline side effects; and 3) Assess changes in affect and cognitive impairment as mediators of extended varenicline therapy's effect on quit rates. We will also explore potential moderators of the effect of extended varenicline treatment on quit rates (e.g., tumor site and stage, time since diagnosis, treatment history, level of nicotine dependence). This study is significant by addressing a population with high smoking rates, which has been under-studied in the area of nicotine dependence treatment, and is at risk for unique adverse tobacco-related health effects. This study is innovative by evaluating the efficacy of extended vs. standard duration varenicline treatment, which may more effectively address unique barriers to cessation in this population. This will also be the first study to use varenicline blood levels as a measure of adherence. There is widespread agreement that evidence-based treatment programs for nicotine dependence among cancer patients are needed. This study may help guide efforts to implement such programs and help determine the benefits of extended treatment duration for nicotine dependence more broadly.

OBJECTIVES

1. Overall Objectives

Aim 1: Compare standard varenicline therapy (12-weeks active then 12-weeks placebo) to extended varenicline therapy (24-weeks active) for treating nicotine dependence among cancer patients.

Hypothesis: Extended varenicline therapy will increase 24- and 52-week biochemically-confirmed 7-day point prevalence abstinence, vs. standard varenicline treatment.

Aim 2: Assess effects of extended varenicline therapy on quality of life (QOL) and varenicline side effects. **Hypothesis:** QOL will be rated higher in the extended therapy group vs. the standard therapy group, and there will be no significant differences between groups in terms of severe side effects.

Aim 3: Assess changes in affect and cognitive impairment as mediators of extended varenicline therapy's effect on quit rates. **Hypothesis:** Improved affect and reduced cognitive impairment will mediate the effect of extended therapy on quit rates.

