Smoking status is assessed using the timeline follow-back method (Brown et al., 1998) as done previously (Lerman et al., 2004; [name] et al., 2010b) and by using breath CO to verify self-report. Participants are considered abstinent if they self-report abstinence (not even a puff of a cigarette) for >7 days prior to the Week 24 and 52 assessment and have a breath CO of <10ppm at the time-point (SRNT, 2002; Hughes et al., 2003). As per convention, participants are assumed to be smoking if they self-report to be smoking at the time-point, cannot be reached to provide data at the time-point, fail to provide a breath sample at the time-point, or provide a breath sample at the time-point that is >10ppm (SRNT, 2002).

Cessation/Smoking Rate: Daily smoking (presence and rate) will be assessed at each visit after Intake Session with the well validated timeline followback method (TLFB). These data can be used to assess

the timing and rates of lapses (smoking episodes not lasting 7 days), recovery events (return to abstinence), and relapse events, as well as to monitor changes in smoking rates (i.e., # cigarettes/day). These data will also be used to compute and assess secondary measures of smoking cessation (e.g., continuous and prolonged abstinence).

Carbon Monoxide (CO) Test: Carbon monoxide will be measured at each in-person visit to confirm smoking status.

Other Smoking Measures (secondary)

As per recommendations (Hughes et al., 2003), we will also assess: prolonged abstinence to Weeks 12, 24, and 52 (relapse is 7 consecutive days of self-reported smoking, after a 2-week grace period), continuous abstinence at Weeks 12, 24, and 52 (no smoking between the quit day and follow-up), time to 7-day relapse (no grace period), smoking rate, and lapse (smoking episodes < 7 days) and recovery (return to 24-hour abstinence) events.

Quality of Life (QOL)

The Short-Form Health Survey (SF-12) will assess QOL (Ware et al., 1996). This scale yields physical and mental subscales, has been used to assess cancer patient QOL (McCorkle et al., 2009), has demonstrated validity and reliability (Gandek et al., 1998), and has been used in smoking cessation trials with cancer patients ([name] et al., 2010a). The SF-12 will be administered at all visits following the Intake Session.

2. Statistical Analysis

Power

Power is provided for the primary aims since the exploratory aim is hypothesis generating. All comparisons are 2-sided.

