Aim 1: The primary analysis is a comparison in Week 24 and Week 52 point prevalence quit rates between standard and extended therapy. For the week 24 comparison, we based our sample size on the expectation that the quit rate in the standard arm would be equal to the Week 24 quit rates reported in past clinical trials of varenicline for participants who received 12 weeks of treatment (i.e., 33%; Gonzales et al., 2006). We also expect to see at least the same effect on week 24 quit rates here as we saw in our past extended treatment trial (i.e., an OR of 1.81 or a difference of ~14%; [name] et al., 2010b). Thus, we have 80% power (alpha .05) with a sample of 374 if the difference between treatment arms in Week 24 quit rates is 14% (i.e., Week 24 quit rates for extended therapy is 47%). For the Week 52 comparison, we can expect a Week 52 quit rate for the extended arm of 56% (Tonstad et al., 2006), vs. 28% for standard treatment (Gonzales et al., 2006), for which we have 99% power (alpha = .05) with n = 374; we are powered to detect a difference at Week 52 of 14% if the present study yields a smaller effect than expected based on past studies.

Aim 2: The primary analysis is a comparison in Week 24 and Week 52 differences in QOL and severe side effects. For QOL, we have 80% power to detect a mean difference of 0.87 in physical QOL and a mean difference of 1.2 in mental QOL at any time-point, effects seen previously ([name] et al., 2010a). For side effects, the analyses will involve a test of non-inferiority since we cannot use standard statistical tests and conclude that a non-significant comparison means that the treatments are equal (i.e., “the absence of evidence is not evidence of absence”). In our past bupropion study ([name] et al., 2010a), 95% of placebo and 88% of bupropion participants reported no severe side effects. Assuming a similar difference, we have 90% power to detect equivalence with a floor of 80%, or an extended group that is 15% < the standard group.

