Aim 1: Compare standard varenicline treatment (12-weeks active then 12-weeks placebo) to extended varenicline treatment (24-weeks active) for treating nicotine dependence among cancer patients. The hypothesized effect of treatment arm (i.e., the difference in quit rates between subjects receiving standard or extended treatment) will be tested by a treatment arm term in a binomial family with logit link (logistic regression) model that possibly includes terms for covariates. Outcomes of the logistic regression analyses will be characterized by odds ratios (e.g., odds of quitting smoking) and 95% confidence intervals. Although quit-rates at the end of 24 and 52 weeks will represent our primary outcome variables, similar logistic regression analyses will be performed for other assessments of quit rates (e.g., quit rates at Weeks 12 and 26). This model will be used for measures of prolonged and continuous abstinence as well. In addition, as many participants will fail to become completely abstinent, the negative binomial family log link for count data will be used to examine the main effects of treatment arm on changes in smoking rate. Time to (recurrent) event models will be fitted using Cox regression, stratified by event sequence, as in [name] et al. (2010).

Aim 2: Assess effects of extended varenicline therapy on QOL and varenicline side effects. Repeated-measures MANOVA will examine differences across treatment arms in mental and physical QOL over the trial. Covariates will be included, such as medical treatment history. We will compare treatment arms in terms of the frequency of severe side effects (individual and total). Logistic regression will test against the lower boundary on percent reporting only mild-moderate (i.e., < severe) side effects. The hypothesis test for equivalence is whether the OR is out of the prescribed range for the difference between the treatment arms.

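### The 80% power claimed for SF-12 differences of 0.87 and 1.2 needs residual SDs of about 3.0 and 4.1 that the plan does not state, and it is not tied to the QOL test the plan specifies

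*Combined protocol and SAP*

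**What the plan says.** All references are to the combined protocol and SAP.

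- **2. Statistical Analysis, Power, Aim 2.** The primary Aim 2 analysis is described as a comparison of QOL at Week 24 and Week 52. For QOL the plan claims "80% power to detect a mean difference of 0.87 in physical QOL and a mean difference of 1.2 in mental QOL", and adds "at any time-point, effects seen previously", citing an earlier bupropion trial. No SD, correlation or QOL-specific alpha is given.
- **Power, opening paragraph and Aim 1.** "All comparisons are 2-sided". For Aim 1, "we have 80% power (alpha .05) with a sample of 374". No allocation ratio is stated.
- **Outcomes Variables, Quality of Life.** On the instrument: "This scale yields physical and mental subscales, has been used to assess cancer patient QOL". No SD is given here either. On timing: "The SF-12 will be administered at all visits following the Intake Session". In Table 2 these are ten visits: Weeks 0, 1, 4, 8, 12, 14, 18, 24, 26 and 52.
- **Data Analysis, Aim 2.** "Repeated-measures MANOVA will examine differences across treatment arms in mental and physical QOL over the trial". Covariates are to be included, with medical treatment history as the example. Baseline SF-12 is not named, nor is a Week 24 or Week 52 contrast, nor the MANOVA term that is the test.
- **Study Medication, Dosing.** Both arms take active varenicline through Day 84; the standard arm switches to placebo on Day 85.
- **Accrual.** About 70% of participants are expected to complete follow-up.

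**The concern.** A power claim for a continuous outcome cannot be checked without an SD. Working backwards from 80% gives the SDs that the claim needs, and nothing in the plan supports them. The claim also concerns one visit at a time, while the only specified analysis spans all ten.

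Aim 2 hypothesises higher QOL under extended therapy. If no difference is found, readers will judge that result against a claimed sensitivity of about one point. If the analysis is run as written, the Week 24 and Week 52 differences that the power section calls primary might not be estimated at all.

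**Working it through.** **Inputs.** From the plan: N = 374, two-sided tests, 80% power, differences 0.87 and 1.2, follow-up about 70%, ten SF-12 visits, treatment identical until Day 85. Assumed: 187 per arm, and alpha 0.05 for QOL (the plan writes it only for Aim 1) with no split over two subscales or two weeks.

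**1. The plan's own figure.** The 80% cannot be reproduced forwards, so solve for the SD.

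- Detectable standardised difference: (1.960 + 0.842) × √(2/187) = 2.802 × 0.1034 = 0.290.
- Implied SDs: 0.87/0.290 = 3.00 and 1.2/0.290 = 4.14.
- Check with the exact t distribution: 79.9% at 0.87 with SD 3.0, and 80.6% at 1.2 with SD 4.1.
- At 70% follow-up (131 per arm): 2.802 × √(2/131) = 0.346, so the SDs must be 2.51 and 3.47.

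Other readings move these values. A one-sided test implies 3.38 and 4.67, against the plan's two-sided rule. A one-sample test on all 374 implies 6.01 and 8.28, but that does not compare arms.

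**2. Sensitivity to the SD.** The SD is an assumption, so a range is shown. Power = Φ(δ/(SD × 0.1034) − 1.960). For example, δ = 0.87 and SD = 8 give Φ(1.052 − 1.960) = 18%.

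| Assumed residual SD | 5 | 6 | 8 | 10 | 12 |
|---|---|---|---|---|---|
| Power, physical (0.87) | 39% | 29% | 18% | 13% | 10% |
| Power, mental (1.2) | 64% | 49% | 31% | 21% | 16% |
| Detectable at 80% power (points) | 1.4 | 1.7 | 2.3 | 2.9 | 3.5 |

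At 131 per arm, SD 5 gives 29% and 49%, and SD 8 gives 14% and 23%.

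**3. Baseline adjustment.** With one SF-12 covariate the residual SD is SD × √(1 − r²). The correlation needed to reach 3.00 (physical) or 4.14 (mental) is:

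- raw SD 5: 0.80 or 0.56
- raw SD 6: 0.87 or 0.72
- raw SD 10: 0.95 or 0.91

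**4. The specified MANOVA.** On the nominal schedule, Weeks 0, 1, 4, 8 and 12 precede Day 85. Take a 0.29 SD effect at the five later visits only, with equal between-visit correlation ρ.

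- *Arm main effect.* The mean effect is 0.29 × 5/10 = 0.145 SD, and the variance of a patient's mean is (1 + 9ρ)/10. At ρ = 0.5, 1.401/√0.55 = 1.889 and Φ(1.889 − 1.960) = 47%. At ρ = 0.7, 1.401/√0.73 = 1.640 and power is 37%.
- *Arm-by-time.* The multivariate F test on 9 df has over 99% power on the same inputs. With differences of 0.87 and 1.2 and an assumed SD of 10, it has 20% and 37% (ρ = 0.5) or 33% and 61% (ρ = 0.7).

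**5. A single-visit contrast adjusted for earlier SF-12,** same 0.29 SD effect:

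- One covariate, residual variance 1 − ρ²: 90% (ρ = 0.5) to 98% (ρ = 0.7).
- Two covariates, residual variance 1 − 2ρ²/(1 + ρ): 93% to 99%.
- In points, at an assumed SD of 10 and ρ = 0.6: 2.90 unadjusted; 2.90 × √0.64 = 2.3 with one covariate; 2.90 × √0.55 = 2.15 with two.

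**The case against.** The strongest reply is that a missing SD is a missing input, not a demonstrated error. The plan takes its effects from an earlier trial, which may also have supplied SDs. A reader might infer that the QOL test is far weaker than stated, or that SDs of 3 and 4 are implausible for SF-12. Both inferences need an SD that no part of the documents gives, so neither is supported. The covariate list is also open-ended, so 3.0 and 4.1 are residual SDs; the mental figure could be met at a raw SD of 5 with a correlation of 0.56.

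A reader might also infer that the MANOVA itself costs power. It does so only if the arm main effect is the test, and the analysis section does not say that it is. The arm-by-time test detects a late effect easily at the implied SDs. Nor can one say that the plan has no single-visit comparison, because the power section names Weeks 24 and 52. The fault is that the two sections disagree.

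Finally, a null result would not mean that the trial could exclude only differences as large as the detectable ones. The 95% half-width is 1.960 × SD × 0.1034, or 1.2 to 2.4 points for SD 6 to 12. The QOL hypothesis is superiority, and Aim 1 sets the sample size.

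What stands is that the stated power cannot be verified and depends heavily on an unstated SD. The arm-by-time test, however powerful, is an omnibus test and does not estimate the Week 24 or Week 52 difference.

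**Conclusion.** The concern holds in this form. The 80% needs residual SDs of about 3.0 and 4.1 with complete data, and about 2.5 and 3.5 at the expected follow-up, and the plan supports neither pair. Whether true power is near 80% or near 10 to 20% depends on an SD that the documents do not give. Separately, the primary QOL comparison in the power section (Weeks 24 and 52) has no counterpart in the analysis section, and the stated power describes no specified test. The back-calculation rests on equal allocation and two-sided 0.05 for QOL; the MANOVA and covariate figures rest on equal correlations of 0.5 to 0.7 and an effect confined to the visits after Day 85.

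**What to change.** 1. Make the QOL analysis the Week 24 and Week 52 arm differences in each SF-12 score, from a model with SF-12 at Week 0 and Week 12 as covariates rather than outcomes. The ten-visit MANOVA can remain as a supporting description. Table 2 allows Week 12 to run a week late, so require the covariate value to precede the Day 85 switch.
2. Replace 0.87 and 1.2 with the detectable difference for that contrast: 0.29 residual SD with complete data, 0.35 at 131 per arm, and the equivalent in points for a stated SD and correlation with their source.
3. State the alpha for two subscales and two weeks, and how missing SF-12 values are handled, including a missing Week 12 covariate.

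The cost is SAP wording, a stated figure that is likely to look less favourable, and some missing Week 12 values to deal with. The measurements are already scheduled, so no new data are needed.

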As in our past (Patterson et al., 2009; [name] et al., 2011) and ongoing (U01 DA020830) varenicline trials, a checklist and open-ended questions assess the incidence and severity of varenicline-related side effects at all time-points following the Intake Session. These assessments monitor safety, and dose reductions or suspension of medication may be indicated based on the side effect reporting. Side effects will be a study outcome and a covariate; overall frequency, changes from pre-treatment baseline (Pre-Quit) and the presence of specific side effects will all be tracked. This measure includes potential varenicline-related psychiatric events (Kuehn, 2008) and cardiovascular side effects.

Varenicline Adherence

Medication adherence will be assessed by self-report using a time-line follow-back method and by pill count and collection of used blister packs at each visit as in past varenicline trials (e.g., Gonzales et al., 2006; Jorenby et al., 2006; Ebbert et al., 2009; Niaura et al., 2008). We will also collect blood (10mL) from 50% of participants enrolled at Penn at Week 4 to assess varenicline levels as an adherence measure and to examine the validity of self-report and pill count data. An adherence measure will represent the proportion of total dose taken (adherence = > 80% of dose taken based on self-report, pill-count, and ng/ml for plasma varenicline; Catz et al., 2011).

Integrity of the Blind

Participants may be likely to notice a change in their physiological and/or psychological state that would be best noted following the two-week washout period (Week 14), and their perception may change after they experience the second potential washout period (Week 26). This follows the questions outlined by [name] et al. (2008).

Program Satisfaction

Given the negative perception that many individuals have of Chantix, understanding patient's satisfaction with the program, and how that might change between weeks 12 (standard duration) and 24 (extended duration), will provide a basis for clinical relevance. These questions were modeled after patient satisfaction questionnaires used for a variety of smoking cessation programs.

Outcomes Variables.

Abstinence (primary)

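### The 90% power stated for the Aim 2 severe-side-effect test is not that of the planned between-arm comparison, and the pass rule and its alpha are not fixed

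*Combined protocol and SAP*

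**What the plan says.** The combined protocol and SAP treats severe side effects as part of the main Aim 2 analysis: "The primary analysis is a comparison in Week 24 and Week 52 differences in QOL and severe side effects". In the Power section, Aim 2, it says that "the analyses will involve a test of non-inferiority", and takes its rates from an earlier bupropion trial in which "95% of placebo and 88% of bupropion participants reported no severe side effects". Assuming a similar gap, it claims "we have 90% power to detect equivalence with a floor of 80%, or an extended group that is 15" percent below the standard group. The paragraph gives no alpha for this test. The Power section opens with "All comparisons are 2-sided", and alpha .05 is attached to Aim 1.

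The Data Analysis section, Aim 2, words the test in two further ways. First, "Logistic regression will test against the lower boundary on percent reporting only mild-moderate" side effects. Second, "The hypothesis test for equivalence is whether the OR is out of the prescribed range for the difference between the treatment arms". No number is given for that range. The Aim 2 hypothesis under Objectives predicts no significant difference between arms in severe side effects.

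**The concern.** A non-inferiority conclusion rests on a numeric margin, a scale and an alpha. Here one paragraph joins a fixed floor and a between-arm margin with the word or, and the analysis section adds an odds-ratio criterion with no value. The floor and the margin are the same rule only if the standard arm is exactly 95% free of severe side effects. That 95% comes from the placebo arm of a bupropion trial, whereas the standard arm here takes active varenicline for 12 weeks, so it is not assured.

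At stake is the trial's safety statement about longer exposure. The power quoted may belong to a different test from the one to be run, and the verdict may depend on which wording is applied once the data are seen.

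**Working it through.** **Inputs.** Total 374 (Power, Aim 1). Allocation is not given in numbers; 1:1, 187 per arm, is assumed, and it returns 79.2% for Aim 1 (33% vs 47%) against the stated 80%. Rates 95% and 88%, floor 80% and margin 15 points are from Power, Aim 2. One-sided 0.025 (implied by two-sided .05) and one-sided 0.05 were both tried.

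**1. Reproducing the 90%: extended arm alone, 88% against a fixed 80%, n = 187.**
- SE under 80%: √(0.80×0.20/187) = 0.02925. SE under 88%: √(0.88×0.12/187) = 0.02376.
- Score test, one-sided 0.05: Φ[(0.08 − 1.645×0.02925)/0.02376] = Φ(1.34) = 91.0%. The exact binomial (pass at 159 or more of 187) also gives 91.0%.
- One-sided 0.025: score 83.0%; exact (161 or more) 82.1%; Wald Φ(0.08/0.02376 − 1.960) = 92.0%.

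So the figure can be recovered, but from a calculation in which the standard arm's data play no part.

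**2. Between-arm comparison, 15-point margin.**
- SE = √(0.95×0.05/187 + 0.88×0.12/187) = 0.0286; (0.15 − 0.07)/0.0286 = 2.796.
- One-sided 0.025: Φ(2.796 − 1.960) = 79.8%. One-sided 0.05: Φ(2.796 − 1.645) = 87.5%.

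| Method | one-sided 0.025 | one-sided 0.05 |
|---|---|---|
| Wald formula | 79.8% | 87.5% |
| Wald, full enumeration | 78.8% | 86.5% |
| Newcombe, full enumeration | 76.1% | 84.9% |
| Farrington-Manning, full enumeration | 74.9% | 84.6% |

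With 40%, 50% or 60% allocated to the standard arm, the Wald formula gives 81.3%, 79.8% and 75.2% at 0.025, and 88.6%, 87.5% and 84.0% at 0.05. Power of 90% would need 252 per arm (0.025) or 205 (0.05) by the same formula. Between-arm variants come near 90% only at one-sided 0.10, a level the documents attach to no test.

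**3. Odds-ratio scale.** The plan gives no value. Converting 15 points at a 95% standard arm gives (0.80/0.20)/(0.95/0.05) = 0.21; at a 90% standard arm it would be (0.75/0.25)/(0.90/0.10) = 0.33, so no single odds ratio equals 15 points.
- At 95/88 the true log OR is −0.952, the limit is −1.558, and the distance is 0.606.
- SE = √[1/(187×0.95×0.05) + 1/(187×0.88×0.12)] = 0.404; 0.606/0.404 = 1.500.
- Power: Φ(1.500 − 1.960) = 32%; Φ(1.500 − 1.645) = 44%.

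**4. Do floor and margin agree?** Full enumeration at one-sided 0.025 (floor: Wilson lower limit above 80%; margin: Newcombe lower limit above −15 points):

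| True rates, standard/extended | passes floor | passes margin | rules disagree |
|---|---|---|---|
| 95/88 (the plan's) | 82.1% | 76.1% | 9.0% + 3.0% = 12.0% |
| 90/83 (sensitivity case, not assumed by the plan) | 15.1% | 61.3% | 46.3% |

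- Extended 157/187, standard 168/187: difference −5.9 points, lower limit −12.8, so the margin is met; the extended arm's lower limit is 78.0%, so the floor is not.
- Extended 161/187, standard 184/187: lower limit for the extended arm 80.4%, so the floor is met; difference −12.3 points, lower limit −18.1, so the margin is not.

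**The case against.** The best defence is that nothing was miscalculated. The floor is named first, the analysis section does speak of a lower boundary on a percentage, and 88% against 80% with 187 patients gives 91.0% at one-sided 0.05. This stands: a reader might infer an arithmetic slip, and the documents do not support that. The mismatch is between the quoted power and the test described.

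It is also fair that one-sided 0.025 is inferred, since the general two-sided statement does not settle the level of a non-inferiority test. At one-sided 0.05 the between-arm figure is 2.5 points or more below 90%, depending on method. Since 95 − 15 = 80, the floor and margin may have been meant as one rule, and the 46% disagreement belongs to rates the plan does not assume. The 12% arises at the plan's own rates.

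Two stronger readings fail. A reader might infer that a safety signal could be hidden; but the plan also compares the frequency of severe side effects between arms directly, and the DSMB reviews side effects by arm. A reader might also subtract the expected losses to follow-up. At about 70% evaluable (131 per arm), power at one-sided 0.025 would be 60–65%, but only if the analysis is limited to patients seen at follow-up. The plan does not say so, and it records side effects at every visit after intake.

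**Conclusion.** The concern holds as a stated power that does not match the planned test, together with a decision rule that is not fixed. At a usual alpha, no between-arm version tried here reaches 90%: about 75–80% (one-sided 0.025) or 85–87.5% (one-sided 0.05) on the risk-difference scale, and about 32% or 44% on the odds-ratio scale under the conversion above. The 1:1 allocation is an assumption, but moving it between 40:60 and 60:40 does not rescue the figure. That floor and margin differ away from a 95% standard arm, and that the odds-ratio range has no number, depends on no power formula. The sample size was set on Aim 1, so this does not show that the trial as a whole is too small. It should be fixed before unblinding.

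**What to change.** State one decision rule, its scale, its confidence-interval method and its one-sided alpha before unblinding, and give the power of that rule. The natural choice is the plan's own 15-point risk difference: extended is non-inferior if the lower limit of the two-sided 95% interval for extended minus standard, in the proportion free of severe side effects, is above −15 points. Power is then about 76% (Newcombe) to 80% (Wald formula), or about 85–87% if the sponsor sets one-sided 0.05. The sponsor should justify the margin. Report the odds ratio descriptively.

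If the sponsor wants to keep the 80% floor, make it an additional stated condition and quote the joint power: at 95/88 and one-sided 0.025 this is 76.1% − 3.0% = about 73%. Dropping the floor has a price, because it loosens the criterion when the standard arm is below 95% (chance of passing at 90/83: about 61% against 15%). The sponsor should say so when choosing.

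Call a positive result non-inferior within the margin rather than equivalent, and reword the Aim 2 hypothesis under Objectives to match. The cost is text in the Power section, the Aim 2 analysis and that hypothesis, plus a less favourable power figure; no new patients or data are needed.

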Participants will also be told that varenicline may impair their ability to perform tasks requiring judgment or motor and cognitive skills and that they should proceed with caution in this regard until they are certain that varenicline does not affect their performance. Participants will be told that varenicline may be associated with somnambulism (sleep walking) that may result in harmful behavior to self, others, or property, and if they notice such behaviors that they should discontinue varenicline and notify the study staff after seeing their medical provider. Participants will also be advised that Chantix may affect their response to alcohol including lower alcohol tolerance, aggressive behavior, or impaired memory following consumption of alcohol. Participants will be instructed to minimize alcohol intake (no more than 3 drinks per occasion or within a 24-hour time period) while taking varenicline. Participants will be advised to inform the study staff if they are taking or plan to take any prescription or over-the-counter drugs. Women will be advised to notify the study staff if they become or intend to become pregnant during the study period. The research team has extensive prior experience conducting smoking cessation trials with varenicline.

Withdrawal. Many individuals who quit tobacco use exhibit a pattern of symptoms associated with withdrawal from tobacco use. These symptoms can include: sadness and anxiety, irritability, difficulty concentrating, anger, appetite change and weight gain, insomnia, and decreased heart rate. Eliminating the risk for these would not be possible, although in most cases these events are short-lived and have low intensity, lasting for 1-2 weeks. Use of varenicline (by all participants for the first 12 weeks of the study) will also minimize the severity of withdrawal symptoms and behavioral counseling will also offer strategies for reducing withdrawal. The study personnel will be trained to recognize these symptoms and educate the participants about them (e.g., their duration, methods for reducing them).

Blood Draws. Blood draws may result in bruising and/or slight bleeding at the needle site. This is rare and happens infrequently. Occasionally, blood drawing results in a feeling of faintness. This too is rare. A trained professional will draw blood, so the chances of these discomforts are minimal. Procedures are in place to ensure that PHI is not linked with the results of this research.

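### The severe-side-effect test is stated as an 80% floor, a 15-point difference and an odds-ratio range with no number; these can give opposite verdicts, and the 15-point margin is not justified

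*Combined protocol and SAP*

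**What the plan says.** Statistical Analysis, Power, Aim 2, makes severe side effects part of the primary comparison for that aim. It states: "For side effects, the analyses will involve a test of non-inferiority". The reason given is that a non-significant difference does not show equality. The only data cited are from an earlier bupropion study: "95% of placebo and 88% of bupropion participants reported no severe side effects". The plan assumes a difference of similar size here and concludes "we have 90% power to detect equivalence with a floor of 80%, or an extended group that is 15% < the standard group".

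Statistical Analysis, Data Analysis, Aim 2, says that logistic regression will test against a lower bound on the percentage with nothing worse than mild to moderate effects. It then adds: "The hypothesis test for equivalence is whether the OR is out of the prescribed range for the difference between the treatment arms". Neither section gives that range a number, or says whether the estimate or a confidence limit decides.

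No alpha is given for this test. The Power section makes all comparisons two-sided and uses 0.05 for Aim 1. Both arms start on active drug; the Withdrawal paragraph under Potential Study Risks refers to "Use of varenicline (by all participants for the first 12 weeks of the study".

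**The concern.** A non-inferiority conclusion is only as good as its margin, and the margin has to be one number on one scale, fixed in advance. Here there are three candidate rules. Two are treated as interchangeable on the strength of a 95% rate that comes from placebo patients, not from patients on 12 weeks of varenicline. The third has no value.

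The power sentence also takes a 7-point excess of severe effects as the truth and plans to conclude equivalence in spite of it. At stake is the Aim 2 safety statement. Depending on the rule applied, the same data could be reported as equivalent or not, and a statistically significant excess could be reported as equivalence.

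**Working it through.** **Inputs.** From Power, Aim 2: 95% and 88% free of severe effects, floor 80%, difference 15 points, power 90%. Total sample 374, taken as 187 per arm (1:1 allocation is assumed). One-sided 0.025 and 0.05 are both tried because the alpha is not stated.

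**1. The plan's 90%.**
- One-sample, extended arm at 88% against a fixed 80%, one-sided 0.05: null SE = √(0.80×0.20/187) = 0.02925; SE at 88% = √(0.88×0.12/187) = 0.02376. Power = Φ[(0.08 − 1.645×0.02925)/0.02376] = Φ(1.34) = 91%. An exact binomial calculation also gives 91%. At one-sided 0.025 the normal approximation gives 83%.
- Two-arm, 15-point margin, 95% versus 88%: SE = √[(0.95×0.05 + 0.88×0.12)/187] = 0.02861. Power = Φ[(0.15 − 0.07)/0.02861 − 1.96] = Φ(0.84) = 79.8%. At one-sided 0.05 it is 87.5%. The Farrington-Manning version gives 73.9% and 83.8%. For 90% the unpooled formula needs 252 or 205 per arm.

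So 90% is matched only by the one-sample test at one-sided 0.05, which does not compare the arms.

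**2. Floor against difference.**

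| Standard arm free of severe effects | Room under an 80% floor | Floor implied by 15 points |
|---|---|---|
| 95% | 15 points | 80% |
| 90% | 10 points | 75% |
| 88% | 8 points | 73% |

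**3. The odds ratio.** The documents give no value. If the margin is converted from 80% versus 95%, it is (0.80/0.20)/(0.95/0.05) = 4/19 = 0.21. This is an assumption, used only to show what a converted margin would do.

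**4. The same 7-point excess under the three rules** (187 per arm, 95% confidence limits).

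Observed 95% versus 88%:
- Floor: lower limit for the extended arm 88 − 1.96×2.376 = 83.3%. Pass.
- Difference: 7 ± 1.96×2.861 = 1.4 to 12.6 points. Pass, although zero is excluded.
- Odds ratio: (0.88/0.12)/(0.95/0.05) = 0.39. SE of the log = √[1/(187×0.0475) + 1/(187×0.1056)] = 0.404; lower limit exp(−0.952 − 1.96×0.404) = 0.17, below 0.21. Fail.

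Observed 88% versus 81%:
- Floor: SE = √(0.81×0.19/187) = 0.02869; lower limit 81 − 5.6 = 75.4%. Fail.
- Difference: SE = √[(0.1056 + 0.1539)/187] = 0.03725; upper limit 7 + 7.3 = 14.3 points. Pass.
- Odds ratio: (0.81/0.19)/(0.88/0.12) = 0.58. SE of the log = 0.292; lower limit 0.33, above 0.21. Pass.

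**5. Size of the margin.** 95 − 80 = 15 points against 95 − 88 = 7 points, a ratio of 2.1. In severe effects, 7 points is 5% to 12%, and 15 points is 5% to 20%.

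**6. How often a pass coincides with a significant excess.** If 95% versus 88% is true, the 15-point rule passes with probability 0.798. The 95% interval fails to exclude zero with probability about Φ(1.96 − 0.07/0.02861) = 0.313. Both a pass and a significant excess occur with probability 0.798 − 0.313 = 0.485, in line with about 49% by simulation.

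**7. Power at equal arms with a 7-point margin** (illustration, one-sided 0.025): Φ[0.07/√(2p(1−p)/187) − 1.96] = 87% at p = 95%, 62% at 90% and 55% at 88%.

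**The case against.** The best defence is that the plan's 90% reproduces against the 80% floor, so the floor may be the intended rule. A standard arm below 95% then makes the test stricter, not looser. Moreover, the converted odds ratio of 0.21 is not the plan's; at the plan's own 95% it is tougher than the 15-point rule. A real excess would not be hidden either: Data Analysis, Aim 2, also compares the arms on the frequency of severe effects, and the monitoring board sees unblinded side effects by arm twice a year. The abstinence outcome is untouched. The expectation of no significant difference is a hypothesis in the Objectives, not a decision rule.

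All of this stands, and it limits the consequence. It does not settle which rule decides. If the floor is the rule, the analysis makes no comparison between arms, contrary to the stated aim and to the power sentence's own second half.

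Four stronger readings are tempting, and the documents do not support them.
- That an extended arm with the full 7-point excess is certain to be called equivalent. It is a probability: about 80% to 91% for the floor and unpooled two-arm calculations, depending on rule and alpha, and only 32% to 44% under the converted odds ratio.
- That the plan allows drops of 25 or 27 points when the standard arm is at 90% or 88%. Those figures follow from 0.21, which the plan never states, and ignore the floor.
- That the 15-point margin was derived from the bupropion trial. The trial supplies the assumed rates; the source of the 80% is not given.
- That 7 points must be the largest acceptable margin. That figure is bupropion against placebo, which is not the contrast here.

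**Conclusion.** The concern holds as an unresolved decision rule with an unjustified margin. The floor and the 15-point difference agree only at a standard-arm rate of 95%, and the odds-ratio range is undefined. The same 7-point excess can pass or fail according to the rule and the standard-arm rate. On the 15-point rule, about half of trials at the plan's assumed rates would declare equivalence with a confidence interval that excludes zero. The stated power of 90% is too high for a two-arm comparison: about 80% at one-sided 0.025 and 87.5% at one-sided 0.05.

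These figures rest on 187 per arm, normal approximations and an alpha the plan does not state; the odds-ratio results also rest on the assumed 0.21. The point affects the Aim 2 safety conclusion only, but it has to be settled before outcomes are compared by arm.

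**What to change.** In both the Power and the Data Analysis text for Aim 2, state one rule: non-inferiority is concluded only if the upper limit of the 95% confidence interval for the risk difference in severe side effects (extended minus standard) is below a single pre-specified margin. Delete the odds-ratio range, and do not keep the 80% floor as a second criterion.

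Justify the margin against a standard arm that also takes active drug. State that the result will not be described as equivalent, or as no difference, when the same interval excludes zero.

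Restate the power for the margin chosen, with the assumed rates, the alpha and the number analysed. For 15 points at 95% versus 88% it is about 80%. If a 7-point margin were chosen and the arms are truly equal, it is 87%, 62% or 55% at 95%, 90% or 88% free of severe effects.

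The change is one of wording and needs no new data. The cost is that the stated power becomes less favourable, and lower still if a tighter margin is adopted.
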